9.2. Sample Size Determination

Approximately 32 participants will be screened to achieve 21 randomly enrolled to either GSK2982772 or placebo in a 2:1 allocation ratio. Replacement participants may be randomised (up to approximately 6) into the study at the discretion of the Sponsor, to ensure that approximately 21 have completed the Week 4 visit.

The primary efficacy endpoint is PASI75 response (achieving ≥75% improvement from Baseline in PASI score)at Week 12. The sample size is based on the difference in PASI75 response rates between GSK2982772 960 mg and placebo.

At Week 12, the expected PASI75 response rate on placebo is approximately 7%. This value represents typical responses seen in this indication [Papp, 2018; Checchio, 2017].

The study will leverage historical placebo data to reduce the uncertainty in the placebo response rate and thus improve operating characteristics of the trial. The historical placebo data will be combined with the trial data via a Bayesian analysis.

With a sample size of 21 participants there is approximately 99% probability of achieving a >97.5% posterior probability that the true treatment difference over placebo >0%, based on an assumed placebo response of 7% and an assumed true treatment difference of 55% and incorporating informative historical placebo data into the analysis. For the placebo arm an informative Beta (3.5, 46.5) distribution with an effective sample size of 50 participants was used. For the active arm a vague Beta (1/3, 1/3) prior is used.

An equivalent power calculation, assuming placebo response of 7% and using a two-sided significance level of 0.05, the proposed sample size of 21 participants gives >90% power to detect a 55% difference in PASI75 response rates between GSK2982772 960 mg versus placebo at Week 12 using a Newcombe score test [Newcombe, 1998] (assuming no historical data is borrowed).

No sample size re-estimation is planned for this study.

Note: "Enrolled" means a participant's, or their legally acceptable representative's, agreement to participate in a clinical study following completion of the informed consent process. Potential participants who are screened for the purpose of determining eligibility for the study, but do not participate in the study, are not considered enrolled, unless otherwise specified by the protocol.

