1.3. Study Design

Overview of Study Design and Key Features	
Design Features	
 Phase 1b/2a, multicentre, randomised, double-blind, placebo-controlled, parallel, repeat dose study of GSK2982772 in participants with active plaque-type moderate to severe psoriasis. The maximum total duration for each participant in the study will be 21 weeks: 
 Screening period of up to 35 days Treatment period of 12 weeks (84 days) Follow-up period for up to 28 days after last dose
Study intervention	
 Participants will receive either GSK2982772 960mg MR QD or placebo for 12 weeks (84 days). No dose modifications or adjustments are permitted per protocol.
Study intervention Assignment	
 Participants will be randomised to receive either GSK2982772 or placebo in a 2:1 ratio. Randomisation will be stratified by prior biologic use.
Interim Analysis	
 One interim analysis is planned to occur when at least six GSK2982772 participants complete the Week 12 visit or withdraw from study treatment.

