5.2.2. Main analytical approach

The primary analysis will be produced for the ITT population.

The summary measure of interest is the difference in PASI75 response rates at Week 12 (Day 85) between GSK2982772 and placebo. Missing values will be imputed as non-responders.

The primary endpoint will be analysed using a Bayesian logistic regression model, details given in [Table 2](#). Summary statistics will be provided for the posterior distribution of the true difference in PASI75 response rate (GSK2982772 vs placebo) as well as posterior probabilities for a range of thresholds.

A non-informative prior will be used for the PASI75 response rate on GSK2982772 and covariates.

An informative prior will be used for the placebo response rate of the form: 90% weight on $Be(5.39, 69)$ and 10% on $Be(1/3, 1/3)$. The prior was derived from historical data from similar clinical trials using meta-analytic predictive prior (MAP) approach, the effective sample size is approximately 63 [[Schmidli, 2014](#)].

In the event that the placebo prior is different from what is presented here, this will be documented in the CSR.

Table 2 Statistical Analysis of Primary Endpoint

Endpoint(s)	

 PASI75 response at Week 12 (Day 85) 	
Analysis Method	
Bayesian Logistic Regression (using informative prior)	
Model Specification	
Outcome	$y_i = \text{Response (0/1) for participant } i$
Predictors	
 Treatment (categorical) Prior Biologic Use (categorical) Baseline PASI score (continuous) 
Unless stated otherwise the predictors (not including study treatment) will be centered around their estimated mean prior to inclusion in the model

Model	$y_i \sim \text{Ber}(p_i)$ $\text{logit}(p_i) = (\text{Treatment=Placebo}) \times \beta_1 + (\text{Treatment=GSK}) \times \beta_2 + (\text{Prior Biologic Use}^*) \times \beta_4 + (\text{Baseline PASI score}^*) \times \beta_5$
Prior distributions for coefficients (β)	β = fixed effect parameters associated to predictors 
 β_1: informative prior such that $\text{logit}^{-1}(\beta_1) \sim$ mixture of Betas* β_2: non-informative prior such that $\text{logit}^{-1}(\beta_2) \sim \text{Beta}(1/3, 1/3)$ Other β_k: non-informative priors of $N(0, SD=100)$ 
*Expected prior is a mixture of $Be(5.39, 69)$ and $Be(1/3, 1/3)$, weighted to 90% and 10% respectively. Final prior will be reported in the CSR.

Model Checking & Diagnostics	
See Section 5.1.1	

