Results Presentation	

 Posterior medians and 95% CrI of true response rate for each treatment group. Posterior medians and 95% CrI for the true difference in proportion of responders (GSK2982772 – placebo) and odds ratios of GSK2982772 to placebo. Probabilities that the true treatment difference is greater than a range of values of interest (e.g. 0%, 20%, 45%, 55%). See OPS outputs list for details. Probabilities that the true response rate on active is greater than a range of values of interest (e.g. 0%, 30%, 55%). See OPS outputs list for details. 	
Interim Analysis	

The interim analysis will estimate the predictive probability of meeting various decision criteria including:
 
 >55% probability that true difference in PASI75 response (GSK2982772 – Placebo) above 45% >97.5% probability that true difference in PASI75 response (GSK2982772 – Placebo) above 0% 	

Predictive probabilities will be calculated via simulation assuming a total sample size of 21 (14:7 for GSK2982772:Placebo).

The parameter posterior distributions from the Bayesian logistic regression analysis of interim data will be used to simulate predicted PASI75 responses for remaining trial subjects. For participants yet to be enrolled, average covariate values will be assumed.

The predicted data will be combined with the observed interim data and the Bayesian logistic model applied to assess the decision criteria. This process will be repeated for each run of the MCMC procedure. The proportion of times the decision criteria is met will be the predicted probability.

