5.8. Interim Analyses

An interim analysis (IA) is planned to occur when at least six participants on GSK2982772 have completed the Week 12 (Day 85) visit or withdrawn from study treatment. The purpose of the IA is for internal decision making about future GSK2982772 trials and assess futility. The study may be stopped for futility if the probability of a positive outcome at the end of the trial is low based on the data available at the IA. The trial cannot be stopped early based on positive efficacy data.

Predictive probabilities will be calculated via simulation. The parameter posterior distributions from the Bayesian logistic regression analysis of interim data will be used to repeatedly simulate PASI75 response for remaining trial subjects. The predicted data will be combined with interim data to assess end of study criteria and calculate the proportion of times the decision criteria are met.

The data will be reviewed by an internal Data Review Committee. The committee will include the study statistician, the study pharmacokineticist and a limited number of GSK staff. A DRC charter will identify the specific staff to form part of the DRC, as well as detail the data to be reviewed, planned analyses, guidelines for the decision rules to be followed and a dissemination plan for interim decisions.

A subset of the outputs for the end of study will be produced for the IA. These will focus on efficacy data including, but not limited to:

- Summaries of PASI response data and change from baseline in PASI score by treatment and visit as outlined in Section [5.3.2](#) (Modified ITT population).
- Bayesian analysis of PASI75 response at Week 12 (Day 85) as outlined in Section [5.2.2](#) (Modified ITT population).
- Summaries of PK data and predicted target engagement as outlined in Section [5.5](#) (PK population).
- Summary of longitudinal model used to predict PASI score and the derived PASI75 at Week 16, outlined in Section [5.5.1](#), (conducted by CPMS on the ITT population).
- Summaries of disposition and psoriatic baseline characteristics (Randomised population).

Safety monitoring of blinded data will be conducted by the internal GSK Safety Review Team (SRT) at regular intervals throughout the study, see Section 8.2 of Protocol.

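### The interim prediction simulates every participant not yet enrolled at average covariates, which on average makes it slightly optimistic; drawing observed covariates instead is a cheap, low-severity improvement

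*SAP*

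**What the plan says.** SAP 5.2.2 (Table 2) fits a Bayesian logistic regression of Week 12 PASI75 response on treatment, prior biologic use and baseline PASI. The two covariates are centred, and each slope has a normal prior with mean 0 and SD 100.

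The interim takes place once at least six active participants have completed Week 12 or stopped treatment. On the prediction, Table 2 says: "Predictive probabilities will be calculated via simulation assuming a total sample size of 21 (14:7 for GSK2982772:Placebo"). Posterior draws from the interim fit supply the missing outcomes; SAP 5.8 says they "will be used to repeatedly simulate PASI75 response for remaining trial subjects". For covariates, Table 2 adds: "For participants yet to be enrolled, average covariate values will be assumed". The simulated and observed data are then combined, the same logistic model is refitted, and the decision criteria are assessed. Two criteria are named:

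- **Criterion A:** more than 97.5% posterior probability that the true difference exceeds 0%.
- **Criterion B:** more than 55% posterior probability that it exceeds 45%.

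The study may be stopped for futility if the predicted chance of success is low. Neither document gives a cutoff, and guidelines for the decision rules are left to the Data Review Committee charter. Neither document justifies the average-covariate rule or plans a check of it.

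**The concern.** Two things go wrong when simulated participants all sit at the covariate mean.

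1. The response probability at the mean covariate is not the mean response probability over real participants. Nobody has a fractional value of prior biologic use.
2. After centring, a participant at the mean has covariate value zero and so tells the refit almost nothing about the slopes. The simulated final analysis then differs from the one the trial will run, in which all 21 participants have real covariate spread.

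At stake is the predictive probability that the Data Review Committee reads when it considers futility. The final analysis and the sample size are untouched.

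**Working it through.** **Inputs from the documents.** 21 participants, 14 active and 7 placebo (SAP Table 2); 2:1 allocation and an interim at six or more active participants (SAP 1.3); placebo rate 7% and difference 55 points, so active 62% (Protocol 9.2); placebo prior 90% Beta(5.39, 69) plus 10% Beta(1/3, 1/3), active prior Beta(1/3, 1/3), slope priors N(0, SD 100) (SAP Table 2).

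**Assumptions not in the documents.** 6 active and 3 placebo at the interim, leaving 14 − 6 = 8 active and 7 − 3 = 4 placebo, 12 in all; 40% prior biologic use; baseline PASI mean 20, SD 6 or 7, floored at 12; 12 or 6 of the remaining 12 not yet enrolled; true active rate 62% or 30%; true covariate effect either zero or moderate (log-odds −1.0 for prior biologic use, −0.7 per SD of PASI).

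**Step 1: the plan's own figure.** Enumerating both binomials with Beta(3.5, 46.5) on placebo gives a 99.7% chance of meeting criterion A, against the stated 99% or so. With the SAP mixture prior it is 98.1%. The planning figure reproduces and does not depend on this point.

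**Step 2: direction.** With centred covariates, logit(p) = β(arm) + x₁β₄ + x₂β₅. At average covariates x₁ = x₂ = 0, so every simulated participant in an arm has p = logit⁻¹(β(arm)). Now take prior biologic use alone, at 40% with log-odds −1.0. The centred values are 0.6 for users and −0.4 for non-users.

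- Active: logit(0.62) = 0.490. Users: 0.490 − 0.6 = −0.110, or 47.2%. Non-users: 0.490 + 0.4 = 0.890, or 70.9%. Mean: 0.4 × 47.2 + 0.6 × 70.9 = 61.4%.
- Placebo: logit(0.07) = −2.587. Users: −3.187, or 4.0%. Non-users: −2.187, or 10.1%. Mean: 0.4 × 4.0 + 0.6 × 10.1 = 7.7% (7.6% unrounded).

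The difference in simulated response rates is 61.4 − 7.6 = 53.8 points with real covariate spread, against 55.0 at average covariates. Fixing covariates is thus mildly optimistic for a moderate slope. This illustrates direction only; it is not a predictive probability.

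**Step 3: full simulation with the refit.** Each interim data set was fitted by MCMC, the remaining outcomes were predicted under each rule, and the model was refitted to all 21 (24 data sets per scenario, 250 predictive draws each). The table shows average-covariate minus resampled predictive probability, in points.

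| True active rate, covariate effect | A, 12 unenrolled | A, 6 unenrolled | B, 12 unenrolled | B, 6 unenrolled |
|---|---|---|---|---|
| 62%, none | 3.0 | 1.9 | 0.9 | 0.9 |
| 62%, moderate | 6.0 | 5.0 | 3.5 | 3.4 |
| 30%, none | 3.8 | 2.0 | 1.2 | 0.7 |
| 30%, moderate | 4.5 | 1.7 | 1.5 | 0.6 |
| Mean (SE) | 4.3 (0.7) | 2.6 (0.7) | 1.8 (0.5) | 1.4 (0.4) |

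For A, the mean absolute change was 4.6 and 3.4 points, against Monte Carlo noise of 1.2 and 1.5. The largest single changes were 0.51 to 0.01 for A and 32 points for B.

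**Step 4: further refit simulations, all 12 unenrolled, PASI SD 7.**

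- Ten covariate patterns at each of 2/6, 3/6 and 4/6 active responders, with 0/3 on placebo: the mean excess was 4.9, 1.9 and 5.0 points for A, and 0.7, 1.8 and 1.3 for B. The largest gap for A, 0.60 against 0.11, came from a near-separated data set. In all 30 patterns the average posterior SD of the PASI slope in the simulated final fit was larger under average covariates.
- 144 data sets: the mean excess was about 5 points for A and 1.6 for B. Measured against covariates drawn from the assumed population, resampling cut the mean absolute error from about 0.087 to 0.055 (A) and from 0.083 to 0.069 (B).

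**The case against.** **The rule matches the SAP's reporting convention.** SAP 5.1.1 reports posterior rates at observed category proportions and mean continuous covariates, so prediction uses the same reference point as the quantity judged. This does not settle the matter. Section 5.1.1 says how to summarise a fitted model, not how to generate participants. Resampled participants can still be summarised at mean covariates after the refit.

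**The scope is narrow.** This stands. The rule covers only people not yet enrolled. The interim waits for 12-week outcomes and no enrolment pause is described, so fewer than 12 may be affected, perhaps none.

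**No decision consequence is shown.** This largely stands. Futility is non-binding, no cutoff is given, and the committee also sees PASI change, PK and longitudinal-model outputs. At assumed cutoffs of 10%, 20% or 30%, 4 to 6 of 96 data sets crossed for A and 1 to 7 of 96 for B. Up to 4 of 96 crossed from noise alone.

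**Resampling has its own weakness.** This also stands. It puts poorly determined slopes directly into every predicted probability, using a small donor pool. The shift is not always optimistic: in one pattern with 2/6 responders, B was 0.56 under averages and 0.69 under resampling.

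**A stronger reading to avoid.** A reader might infer that average covariates make the result depend on which interim participants responded rather than on how many, and that resampling cures this. It does not. With the refit at 3/6 responders, B ranged over 0.16–0.88 under averages and 0.07–0.95 under resampling in one set of patterns, and over 0.25–0.67 and 0.21–0.67 in another. The likelier driver is the very wide slope prior with nine participants. Much larger gaps between the rules appear if the final criterion is computed from response counts without covariates, but the SAP refits the covariate model.

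**Conclusion.** The point holds at low severity. With all 12 remaining participants unenrolled, the average-covariate rule raises the predictive probability by about 4 to 5 points for A and 1 to 2 points for B. With 6 unenrolled the figures are about 2.6 and 1.4; with enrolment complete there is no effect. The error usually makes a futility stop less likely. It is occasionally tens of points, mainly where the interim data nearly separate.

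These sizes rest on the assumed interim split, covariate distribution and covariate effects, none of which the documents give. The documents do not support a claim that the futility look is invalid or that a wrong stop is likely. The 99% planning figure and the primary analysis are unaffected.

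**What to change.** In SAP Table 2, replace the average-covariate sentence with:

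> For participants yet to be enrolled, baseline PASI and prior biologic use will be drawn with replacement, as a pair, from all participants randomised to date, independently in each MCMC draw.

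Using everyone randomised, not only those with Week 12 data, enlarges the donor pool: 9 donors if 12 are unenrolled, 21 − 6 = 15 if 6 are. A weaker alternative is to keep the present rule and show the committee both versions.

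The cost is one SAP sentence and about one line of simulation code, settled before the first unblinded look. It needs no extra participants or data. The limit is that the donor pool stays small and the slopes stay unstable under the N(0, SD 100) priors, so the change reduces the error without removing it.

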5.2.3. Sensitivity analyses

Where informative priors have been used, a sensitivity analysis using vague priors (no historical borrowing) will also be produced.

Additional sensitivity analyses to assess the impact the missing data handling for binary data may be produced, such as using a LOCF approach to missing data.

5.2.4. Supplementary analyses

A supplementary analysis where the primary analysis is repeated using the Modified ITT population may be produced to assess the treatment effect in subjects able to complete at least 4 weeks of treatment. A frequency table of PASI response using this population would also be produced.

Off-treatment PASI data, collected following treatment discontinuation prior to Week 12, may be used for additional supplementary analyses if available.

5.2.5. Subgroup analyses

No formal subgroup analysis is planned. Descriptive statistics in the form of a frequency table of PASI75 response by prior biologic use will be produced.

5.3. Secondary Endpoint(s) Analyses

5.3.1. Definition of endpoint(s)

The secondary efficacy endpoints are:

Categorical endpoints

- PASI50, PASI90 and PASI100 response at Week 12 (Day 85), where PASIX response is defined as a reduction in PASI score from baseline of at least X%.
- sIGA response at Week 12 (Day 85), defined as **cci** (0) or **cci** (1).

Continuous endpoints

- Change from Baseline in PASI scores at Week 12 (Day 85)
- Change from Baseline in psoriatic BSA at Week 12 (Day 85).

5.3.2. Main analytical approach

Categorical endpoints

The proportion of participants achieving additional PASI responder endpoints of interest (PASI50/90/100) will be summarised by treatment arm and visit. Missing values will be imputed as non-responders. Credible intervals for response rates will be included (using $Be(1/3, 1/3)$ prior for all treatment arms and visits).

The sIGA scores will be summarised as categorical data with the proportion of participants achieving each sIGA score being presented by treatment group and visit. The proportion of sIGA **cci** (0) or **cci** (1) will also be presented, with missing values imputed as non-responders. Credible intervals for response rates will be included (using $Be(1/3, 1/3)$ prior for all treatment arms and visits).

Line plots of proportion of responders (with 95% CrI) over time by treatment group will be produced for both PASI and sIGA responder endpoints.

A Bayesian logistic regression approach will be used to assess response rates at Week 12, details given in [Table 3](#).

Continuous endpoints

Both secondary and exploratory objectives of BSA and PASI score will be investigated using the same Bayesian repeated measures model (MMRM) analysis.

Summary statistics by treatment and visit will be provided for change from baseline in both PASI score and BSA. A summary of percentage change in PASI will also be provided.

A Bayesian MMRM approach will be used to account for the repeated visits (details given in [Table 4](#)). This approach assumes missing values are MAR.

Line plots of posterior means (\pm SD) from the MMRM analysis over time by treatment group will be provided.

Table 3 Statistical Analysis of Categorical Secondary Endpoint(s)

Endpoint(s)	

 • Proportion of PASI50, PASI90 and PASI100 responders at Week 12 (Day 85) • Proportion of sIGA ^{CCI} (0) or ^{CCI} (1) at Week 12 (Day 85) 	
Analysis Method	
Bayesian Logistic Regression	
Model Specification	
Outcome	y_i = Response (0/1) for participant i
Predictors	
 • Treatment (categorical) • Prior Biologic Use (categorical) • Baseline score (sIGA to be treated as continuous) 
Unless stated otherwise the predictors (not including study treatment) will be centered around their estimated mean prior to inclusion in the model

Model	$y_i \sim \text{Ber}(p_i)$ $\text{logit}(p_i) = (\text{Treatment}=\text{Placebo}) \times \beta_1 + (\text{Treatment}=\text{GSK}) \times \beta_2 + (\text{Prior Biologic Use}^*) \times \beta_4 + (\text{Baseline PASI score}^*) \times \beta_5$
Prior distributions for coefficients (β)	β = fixed effect parameters associated to predictors 
 • β_1 & β_2: non-informative prior such that $\text{logit}^{-1}(\beta_k) \sim \text{Beta}(1/3, 1/3)$ • Other β_k: non-informative priors of $N(0, \text{SD}=100)$
Model Checking & Diagnostics	
See Section 5.1.1	
Results Presentation	

 • Posterior medians and 95% CrI of true response rate for each treatment group. • Posterior medians and 95% CrI for the true difference in proportion of responders (GSK2982772 – placebo) and odds ratios of GSK2982772 to placebo. • Probabilities that the true treatment difference is greater a range of values of interest (e.g. 0, 20, 40). See OPS outputs list for details. 	

Table 4 Statistical Analysis of Continuous Secondary Endpoint(s)

Endpoint(s)	

 • Change from Baseline PASI scores at Week 12 (Day 85) • Change from Baseline in psoriatic BSA at Week 12 (Day 85) 	
Analysis Method	
Bayesian GLMM with natural link (MMRM equivalent)	
Model Specification	
Outcome	y_i = vector of change from baseline for participant i
Predictors	
 • Treatment (categorical) • Visit (categorical) • Treatment*visit (categorical) • Prior Biologic Use (categorical) • Baseline (continuous) • Baseline*visit (continuous) 
Unless stated otherwise the predictors (not including study treatment or visit) will be centered around their estimated mean prior to inclusion in the model

Model	$y_i \sim MVNormal(\mu_i, \Sigma)$ $\mu_i = X_i \beta$
Prior distributions for coefficients (β)	β = fixed effect parameters associated to predictors 
 • β_k: non-informative prior of $N(0, SD=100)$
Prior distributions for random effects (b)	
 • $\Sigma \sim$ Inverse Wishart (J, S), with J = number of visits (degree of freedom), S = identity matrix 
Note: If convergence issues occur, an alternative covariance matrix structure may be used, for example a compound symmetric structure, to help improve convergence.

Model Checking & Diagnostics	
See Section 5.1.1	
Results Presentation	

 • Posterior mean, SD and 95% CrI will be presented for each treatment by timepoint interaction. • Posterior mean treatment differences (GSK2982772 – placebo) and associated 95% CrI will be produced for each timepoint. • Probabilities that the true treatment difference at each visit is greater a range of values of interest (e.g. 0, 100) may be provided. See OPS outputs list for details. • Outputs produced will include results for earlier timepoints in addition to the objective specified timepoint of Week 12 (Day 85). 	

